#### **D.5.5. Follow-Up Contact**

We maintain a log of all programs in our sampling frame that returned enrollment forms. On August 5, 2019, a reminder email was sent to program directors and department chairs for programs in the sampling frame that had not yet returned their forms. On August 13, 2019, a reminder email was sent to designated institutional officials for programs in the sampling frame that had not yet returned their forms. Starting on August 28, 2019, the co-PIs began contacting the remaining programs by email and/or text message to encourage them to enroll, ask about the barriers to enrollment, and offer facilitation (e.g., by extending the deadline, providing IRB or protocol materials). Based on feedback from New York State programs, on September 4, 2019, a clarifying email was sent to all unenrolled New York State programs to notify them that they were eligible for the SECOND Trial; unlike the FIRST Trial, New York State legislation does preclude participation. On September 4, 2019, the members of the Resident Advisory Committee were provided with a list of unenrolled programs so that they could contact residents that they personally know and encourage them to speak with their program directors about enrolling. On September 5, 2019, programs that had completed a Program Wellness Initiatives Inventory Survey, but not yet submitted an enrollment form were contacted. On September 9, 2019, the members of the Faculty Advisory Committee were provided with a list of unenrolled programs to similarly encourage enrollment. On September 25, 2019, a final reminder email was sent to unenrolled programs.

#### **D.5.6. Enrollment Closure**

Enrollment for the SECOND Trial officially closed on August 30, 2019, but was extended until October 31, 2019, given a large number of interested programs that were still in the process of obtaining internal approvals.

#### **D.5.7. Enrollment Materials**

Please see **Appendix 3** for facsimiles of recruitment materials (including, but not limited to contact emails, informational outreach materials, and the enrollment form/participation agreements).

## **D.6. STUDY UNITS**

### **D.6.1. Unit of Randomization**

The unit of randomization is the general surgery residency program. Eligible residency programs will be randomized to Control or Intervention.

### **D.6.2. Level of Observation**

The unit of observation is the unit or entity upon which data were collected. The units of observation in this study are:

- Residency program
- Patient (secondary analysis)
- Resident (secondary analysis)

## **D.7. RANDOMIZATION PROCEDURES**

We plan to use stratified cluster-randomization to allocate general surgery residency programs to the two study arms to help ensure balance of programs with respect to prior levels of resident burnout. We anticipate that there is a range of extant wellness activities across general surgery residency programs prior to the start of the SECOND Trial. The concern is that chance allocation may result in an imbalance of residency programs across study arms with respect to previous experience/activity in addressing resident wellness issues.

### **D.7.1. Cluster Unit of Randomization**

The unit of randomization will be the general surgery residency program.

### **D.7.2. Definition of Randomization Strata**

Using data from the 2019 ABSITE Survey, we will compute mean resident burnout scores (§C.2) within each residency program. Programs will then be stratified into quartiles based on mean resident burnout scores in 2019. Programs that do not have 2019 ABSITE data will be grouped into a fifth stratum (“no previous data”).

The choice to define randomization strata on the basis of prior levels of resident burnout in programs was motivated by a desire to balance programs across study arms according to previous exposure to wellness activities and programming. We assume that extant levels of program engagement in issues of resident wellness will be reflected – at least to some degree – in mean levels of burnout within programs.

The number of strata was chosen based on a consideration of: avoiding thin strata; avoiding the inclusion of an excessive number of additional parameters in the final analytic models; and the ability to reduce between-program variance. Quartiles were chosen over tertiles because inclusion of quartiles in preliminary models showed that quartiles were slightly more effective in reducing between-program variance by (86% vs. 75%) compared to empty models (§D.8).

### **D.7.3. Randomization Procedure and Treatment Assignment**

General surgery residency programs that enroll in the SECOND Trial will be grouped into four strata:

- Stratum 1 – Quartile 1, 2019 ABSITE program mean resident burnout scores
- Stratum 2 – Quartile 2, 2019 ABSITE program mean resident burnout scores
- Stratum 3 – Quartile 3, 2019 ABSITE program mean resident burnout scores
- Stratum 4 – Quartile 4, 2019 ABSITE program mean resident burnout scores
- Stratum 5 – *No data* on 2019 ABSITE program mean resident burnout score

Residency programs within each stratum will be assigned a unique, randomly-generated integer using a random-number generator. Residency programs within each stratum will be ordered in ascending order according to their randomly-assigned number. Four separate, blinded lists will be constructed containing the randomly-generated numbers corresponding to each program within each of the four strata. These blinded lists will be given to the Project Coordinator, who, with another Study Team member to be appointed, will alternately assign programs to Control or to Intervention. They will decide to start with control or intervention on the basis of a coin toss. An observer unaffiliated with the study will be present.

Once study arm assignments have been made for each of the four blinded lists, the blinded lists will then be sent back to the Statistical Analyst who will then unblind the lists. Final, unblinded residency program study arm assignments will be sent back to the Project Coordinator, so that participating programs may be notified of their study arm assignment. Study arm assignments will not be made public, but programs participating in the trial will be listed on the SECOND Trial website and [www.clinicaltrials.gov](http://www.clinicaltrials.gov).

## **D.8. SAMPLE SIZE/POWER CALCULATIONS**

### **D.8.1. Data for Sample Size/Power Calculations**

Data for power calculations came from the 2019 ABSITE Survey and are based on data from residents who were clinically active. Calculations were made for the primary endpoint only, burnout (§C.1 and §E.1).

In the 2019 ABSITE survey data, complete data on burnout survey items Q15A-Q15F and burnout scores were available for 5,962 clinically active residents from 300 programs. Clinically inactive residents were excluded, as were residents that had incomplete data on burnout survey items Q15A-Q15F. Program sizes, measured in terms of the number of respondents, ranged from 3 to 54, with a mean of 19.873 (SD=9.647).

Because we intend to randomize programs within strata defined on the basis of program-level mean burnout using prior data, we also used data from the 2018 ABSITE survey in order to define program-level strata for our preliminary models from which parameters were obtained for power calculations.

### **D.8.2. Outcome Measurement**

As discussed in §E.1.2.3., our outcome measure in the SECOND Trial is an item response theory (IRT) derived measure of the latent burnout trait (theta) that has been linearly transformed into T-scores. This will be our outcome measure in our models, and this is the measure that we use for our power calculations.

A complete description of how T-scores were derived in the 2019 ABSITE data is given in §E. In 2019, the mean burnout T-score was 50.008, with a standard deviation of 9.500. Burnout T-scores ranged from a minimum of 32.078 to a maximum of 80.367.

### **D.8.3. Preliminary Models**

Using ABSITE data from 2018, we computed IRT-derived T-scores for residents (2018 ABSITE survey items Q11A-Q11F). We then computed program-level mean burnout T-scores, and then stratified programs into quartiles based on these program-level mean burnout scores. These 2018 burnout quartiles were merged back to the 2019 ABSITE data. Programs that were missing in the 2018 ABSITE were grouped into a fifth stratum.

We estimated (a) a two-level (“empty”) hierarchical linear model with random program intercepts; (b) an “unadjusted” hierarchical model adjusting only for program strata (quartile of 2018 burnout scores); and (c) an “adjusted” model that controlled for resident gender (female (reference male)); post-graduate year (PGY); resident relationship status; resident race (nonwhite (reference white)) and program quartile of burnout based on program-level mean burnout scores from 2018, program geographic region (Southeast, Midwest, Southwest, West (reference Northeast)); program type (community, military (reference academic)), and program size.

The intraclass correlation from the empty model was 0.082, suggesting that roughly 8% of total variance in resident burnout scores in 2019 were attributable to the program level. Controlling for program quartile of 2018 mean burnout scores in the “unadjusted” model reduced the program-level (Level-2) variance component by 75%, from 7.413 to 1.821, and reduced the ICC to 0.021. Including additional resident and program covariates reduced the Level-2 variance component by 86% compared to

the empty model. The ICC in the adjusted model was 0.012 – i.e., approximately 1% of the variance in resident burnout scores was attributable to the program level after controlling for a program’s prior year mean burnout T-score and resident/program characteristics.

The population-averaged mean burnout score estimated from the empty model was 49.753 (SD=9.137, square root Level 1 residual variance). The mean resident burnout score from the “unadjusted model” with controls for 2018 program mean burnout was 46.970 (SD=9.150). The mean resident burnout score from the adjusted model was 45.933 (SD=9.027, Level 1 residual).

Using the constant estimated from the adjusted model as an estimate of the mean burnout score in Control (45.933) and the standard deviation of the Level-1 error component as the estimate of the standard deviation (9.027) around mean burnout scores in Control and assuming  $\alpha_{final}=0.0443$  for the final analysis, 80% power and  $ICC=0.012$ , we computed minimal detectable differences for a variety of hypothetical sample sizes, as reported in EXHIBIT D.8-B.

The scenario yielding the smallest detectable difference in adjusted mean burnout scores would be one in which there are 300 programs total, 150 programs in each arm with a mean of 25 residents per program. In this scenario, given our assumptions, we expect to be powered at 80% to detect a relative difference in mean burnout scores of -1.46%.

In a conservative scenario with 100 programs randomized to each study arm (200 programs total) and an average of 15 residents per program, we expect to be powered at 80% to detect a relative difference in mean burnout scores of -2.22%.

In a moderate scenario with 110 programs randomized to each study arm (220 programs total) and an average of 20 residents per program, we expect to be powered at 80% to detect a relative difference in mean burnout scores of -1.87%.

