**EXHIBIT D.8.A. Preliminary Burnout Model for Power Calculations**

		Coefficient (95% CI)	
	Empty Model	Unadjusted Model	Adjusted Model
Program Strata (ref: Stratum 1)			
Stratum 2	---	2.510 (1.643-3.377)	2.134 (1.261-3.007)
Stratum 3	---	3.442 (2.575-4.309)	3.076 (2.202-3.951)
Stratum 4	---	6.258 (5.384-7.131)	5.598 (4.719-6.477)
Stratum 5	---	0.273 (-0.885-1.430)	---
Female (ref: male)	---	---	2.064 (1.544-2.583)
PGY level (ref: PGY1)			
PGY2	---	---	0.479 (-0.276-1.233)
PGY3	---	---	-0.101 (-0.874-0.673)
PGY4	---	---	-0.607 (-1.393-0.179)
PGY5	---	---	-0.548 (-1.350-0.253)
Relationship status (ref: not in relationship)			
Married	---	---	0.265 (-0.408-0.938)
In a relationship	---	---	0.965 (0.279-1.651)
Divorced/widowed	---	---	-0.318 (-2.203-1.566)
Non-white (ref: white)	---	---	-1.512 (-2.056- -0.968)
Geographic region (ref: Northeast)			
Southeast	---	---	0.124 (-0.690-0.939)
Midwest	---	---	0.307 (-0.484-1.098)
Southwest	---	---	0.033 (-0.958-1.023)
West	---	---	0.064 (-0.299-1.582)
Program type			
Community	---	---	-0.069 (-0.810-0.672)
Military	---	---	-0.322 (-1.985-1.341)
Program size	---	---	0.125 (-0.056-0.306)
Constant	49.753 (49.356-50.150)	46.970 (46.325-47.615)	45.933 (44.461-47.405)
Variance components			
Level-2	7.413 (5.627-9.767)	1.821 (1.010-3.285)	1.010 (0.417-2.446)
Level-1	83.483 (80.459-86.622)	83.721 (80.686-86.870)	81.485 (78.303-84.795)
Intraclass correlation	0.082	0.021	0.012
N residents	5962	5962	5075
N programs	300	300	237
Likelihood ratio test vs. linear model (x2)	172.20	18.29	6.94
P value	P<0.001	P<0.001	P=0.004

Data: 2019 (version 2) and 2018 ABSITE Survey data. The dependent variable is an IRT-derived burnout T-score based on 6 survey items corresponding to emotional exhaustion and depersonalization subscales (2019 ABSITE survey items Q15A-Q15F, see §E.1 for details). Program strata refers to program quartile based on program mean 2018 ABSITE burnout T-scores. The 5th stratum contains programs that had missing 2018 ABSITE data and were thus not ranked in a quartile. However, this stratum dropped out of the adjusted model due to collinearity.

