#### EXHIBIT D.8.B Minimal Detectable Differences for Primary Analysis under Varying Sample Size Scenarios

Number of Programs (Clusters) per Arm	Number of Residents per	Usual Care Mean Burnout	Estimated Intervention	Minimal Detectable Difference	Relative Difference (%)

	Program (Mean Cluster Size)		Mean Burnout		
150	25	45.93	45.26	-0.67	-1.46%
150	20	45.93	45.19	-0.74	-1.61%
150	15	45.93	45.10	-0.83	-1.81%
125	25	45.93	45.19	-0.74	-1.61%
125	20	45.93	45.12	-0.81	-1.76%
125	15	45.93	45.02	-0.91	-1.98%
110	25	45.93	45.14	-0.79	-1.72%
110	20	45.93	45.07	-0.86	-1.87%
110	15	45.93	44.96	-0.97	-2.11%
100	25	45.93	45.10	-0.83	-1.81%
100	20	45.93	45.03	-0.90	-1.96%
100	15	45.93	44.91	-1.02	-2.22%

NOTES: Minimal detectable difference from adjusted estimate of mean burnout scores, assuming mean burnout T-scores in Usual Care=45.933, SD in both arms=9.027, ICC=0.012, alphafinal=0.0443 and power=80%, based on preliminary estimates in EXHIBIT D.8-B. Relative difference is expressed as a percent of Usual Care mean.

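### The power section takes a regression constant (45.933) for the Control mean, and its detectable differences belong to a two-sided test while the primary test is one-tailed

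*SAP*

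**What the plan says.** D.8.2 reports the observed outcome: "In 2019, the mean burnout T-score was 50.008, with a standard deviation of 9.500". D.8.3 then fits three models to the 2019 data and reports a mean for each:

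- Empty model: "The population-averaged mean burnout score estimated from the empty model was 49.753".
- Strata-only model: the mean "with controls for 2018 program mean burnout was 46.970 (SD=9.150").
- Adjusted model: "The mean resident burnout score from the adjusted model was 45.933 (SD=9.027, Level 1 residual").

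In Exhibit D.8.A the last two figures stand in the row for the constant, and the strata rows are headed "Program Strata (ref: Stratum 1").

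The power calculation then proceeds: "Using the constant estimated from the adjusted model as an estimate of the mean burnout score in Control (45.933"), with SD 9.027, ICC 0.012, alpha 0.0443 and 80% power. D.8.3 gives its three power results only as percentages; for 110 programs per arm with 20 residents each, "we expect to be powered at 80% to detect a relative difference in mean burnout scores of -1.87"%. Exhibit D.8.B carries 45.93 as the Usual Care mean in all 12 rows, and its note says: "Relative difference is expressed as a percent of Usual Care mean".

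Neither D.8.3 nor the exhibit says whether 0.0443 is one- or two-sided. F.3.1.2 calls the primary result significant at a one-tailed p below 0.0443.

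**The concern.** The constant of a model with categorical covariates is the expected score when every such covariate is at its reference level. For the adjusted model that is a white male PGY1 resident, not in a relationship, in a Northeast academic program in the lowest-burnout quartile, with program size at its zero point. No arm of the trial is expected to average that value. A reader of D.8 would take 45.93 as the anticipated Control level, and the three power statements are percentages of it.

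The second question is which test the exhibit describes. If the detectable differences were computed two-sided, the stated 80% is not the power of the test in F.3.1.2. The SAP would then support two readings of the primary test, and that choice could decide a borderline result.

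**Working it through.** **Inputs.** SD 9.027, ICC 0.012, alpha 0.0443 and power 80% (Exhibit D.8.B notes); k programs per arm and m residents per program (exhibit rows); coefficients and constants (Exhibit D.8.A); means 50.008 (D.8.2), 49.753 (D.8.3) and 50.48 (Exhibit D.9, Control programs).

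**Reproducing the printed detectable differences.**

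SE = SD × √(2 × [1 + (m − 1) × ICC] / (k × m)), and MDD = (z_alpha + 0.8416) × SE, where z_alpha = 2.011 two-sided or 1.703 one-tailed at 0.0443.

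For 110 × 20 the design effect is 1 + 19 × 0.012 = 1.228, so SE = 9.027 × √(2 × 1.228 / 2200) = 0.3016.

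- Two-sided: 2.853 × 0.3016 = 0.8605 (printed 0.86).
- One-tailed: 2.544 × 0.3016 = 0.767.

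All 12 rows, with power at the printed difference from Φ(MDD/SE − 1.703):

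| Programs × residents | Printed MDD | Two-sided 0.0443 | One-tailed 0.0443 | One-tailed power at printed MDD |
|---|---|---|---|---|
| 150 × 25 | 0.67 | 0.675 | 0.60 | 87.1% |
| 150 × 20 | 0.74 | 0.737 | 0.66 | 87.7% |
| 150 × 15 | 0.83 | 0.830 | 0.74 | 87.5% |
| 125 × 25 | 0.74 | 0.739 | 0.66 | 87.5% |
| 125 × 20 | 0.81 | 0.807 | 0.72 | 87.7% |
| 125 × 15 | 0.91 | 0.909 | 0.81 | 87.6% |
| 110 × 25 | 0.79 | 0.788 | 0.70 | 87.6% |
| 110 × 20 | 0.86 | 0.860 | 0.77 | 87.5% |
| 110 × 15 | 0.97 | 0.969 | 0.86 | 87.6% |
| 100 × 25 | 0.83 | 0.827 | 0.74 | 87.7% |
| 100 × 20 | 0.90 | 0.902 | 0.80 | 87.3% |
| 100 × 15 | 1.02 | 1.016 | 0.91 | 87.7% |

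The two-sided form matches every row within 0.005. The one-tailed form matches none and is about 11% smaller (2.544/2.853 = 0.892).

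**Is the constant a mean?** Averaging the strata-only model over four equal quartiles gives 46.970 + (0 + 2.510 + 3.442 + 6.258)/4 = 50.02, essentially the observed 50.008. If Stratum 5 (coefficient 0.273) is given a 21% weight, assuming that it holds the 300 − 237 = 63 programs absent from the adjusted model, the result is 49.44. Either way 46.970 is the level of Stratum 1. For the adjusted model the strata alone raise the constant to 45.933 + (0 + 2.134 + 3.076 + 5.598)/4 = 48.64, before any other covariate is averaged.

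**Effect on the percentages.** All 12 printed percentages equal MDD/45.93. Re-based:

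| Scenario | MDD | Printed | On 49.753 | On 50.008 | On 50.48 |
|---|---|---|---|---|---|
| 150 × 25 | 0.67 | 1.46% | 1.35% | 1.34% | 1.33% |
| 110 × 20 | 0.86 | 1.87% | 1.73% | 1.72% | 1.70% |
| 100 × 15 | 1.02 | 2.22% | 2.05% | 2.04% | 2.02% |

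The inflation factor is 49.753/45.933 = 1.083, 50.008/45.933 = 1.089 or 50.48/45.933 = 1.099.

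**The case against.** The base error touches no design result. The differences in points are right and printed beside the percentages, the sample size does not move, and the percentages shift by only 0.12 to 0.18 points on 50.008. The SAP also discloses that it uses the constant, prints the reference categories and prints the other means, so a careful reader can undo the choice. The division itself is correct; only the base is poor. All of this stands, and it limits the consequence. It does not make the label right: D.8.3 calls both constants mean scores, and its prose gives no result in points.

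The comparison means are not strictly like for like. The 50.48 averages programs rather than residents, while 49.753 and 50.008 come from 5,962 residents in 300 programs, against 5,075 in 237 for the adjusted model. The marginal mean of the adjusted sample cannot be recovered from the SAP, so the 8 to 10% inflation is a bracket, not an exact error.

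On sidedness, D.8 nowhere says two-sided; that is inferred. A match in 12 rows against none leaves little doubt. A two-sided calculation beside a one-tailed test is also conservative, so no power is lost.

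Finally, the 87 to 88% keeps the exhibit's simplifications: equal cluster sizes and the Level-1 SD. With the cluster-size variation in D.8.1 (9.647/19.873 = 0.485), a design effect of 1 + [(1 + 0.485²)m − 1] × 0.012 and the total SD √(81.485 + 1.010), power at the printed differences is about 85 to 86% one-tailed and 77 to 78% two-sided. That is a fair refinement, but the mismatch between exhibit and test remains.

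**Conclusion.** Both parts hold. The 45.933 in D.8.3 and Exhibit D.8.B is a reference-level constant, 3.8 to 4.5 points below every mean that the SAP reports. The two mean columns, all 12 relative differences and the three power sentences therefore rest on a wrong base, and the percentages are about 8 to 10% too large relative to their proper value. The equal-quartile averaging is illustrative, and the coding of program size is not given, but neither changes this conclusion.

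The detectable differences were, by reproduction, computed two-sided, while F.3.1.2 tests one-tailed. On the exhibit's own inputs the stated 80% is about 87 to 88% for the stated test. The errors affect how the power is reported and which test it describes; they call for no change in the number of programs.

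**What to change.** In D.8.3, describe 46.970 and 45.933 as model constants at reference levels, not as mean burnout scores. State the three power results in the T-score points already in Exhibit D.8.B: 0.67 (150 × 25), 0.86 (110 × 20) and 1.02 (100 × 15). Drop the two mean columns and the percentage column: the T-score is 50 + 10 × theta, so its origin is arbitrary and a percentage of any mean says little. If percentages are kept, base them on a mean near 50 and name its source.

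State the sidedness of 0.0443 in D.8 and reconcile it with F.3.1.2 and F.4. Either the primary test becomes two-sided at 0.0443 and the printed differences stand on the exhibit's assumptions, or it stays one-tailed and the exhibit takes the one-tailed differences (0.60, 0.77 and 0.91 for the three headline scenarios).

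The cost is three sentences, one table and a line on sidedness. The two-sided choice has a price: at 0.86 points with 110 × 20, power is 80% rather than about 87%.

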**EXHIBIT D.8.A. Preliminary Burnout Model for Power Calculations**

		Coefficient (95% CI)	
	Empty Model	Unadjusted Model	Adjusted Model
Program Strata (ref: Stratum 1)			
Stratum 2	---	2.510 (1.643-3.377)	2.134 (1.261-3.007)
Stratum 3	---	3.442 (2.575-4.309)	3.076 (2.202-3.951)
Stratum 4	---	6.258 (5.384-7.131)	5.598 (4.719-6.477)
Stratum 5	---	0.273 (-0.885-1.430)	---
Female (ref: male)	---	---	2.064 (1.544-2.583)
PGY level (ref: PGY1)			
PGY2	---	---	0.479 (-0.276-1.233)
PGY3	---	---	-0.101 (-0.874-0.673)
PGY4	---	---	-0.607 (-1.393-0.179)
PGY5	---	---	-0.548 (-1.350-0.253)
Relationship status (ref: not in relationship)			
Married	---	---	0.265 (-0.408-0.938)
In a relationship	---	---	0.965 (0.279-1.651)
Divorced/widowed	---	---	-0.318 (-2.203-1.566)
Non-white (ref: white)	---	---	-1.512 (-2.056- -0.968)
Geographic region (ref: Northeast)			
Southeast	---	---	0.124 (-0.690-0.939)
Midwest	---	---	0.307 (-0.484-1.098)
Southwest	---	---	0.033 (-0.958-1.023)
West	---	---	0.064 (-0.299-1.582)
Program type			
Community	---	---	-0.069 (-0.810-0.672)
Military	---	---	-0.322 (-1.985-1.341)
Program size	---	---	0.125 (-0.056-0.306)
Constant	49.753 (49.356-50.150)	46.970 (46.325-47.615)	45.933 (44.461-47.405)
Variance components			
Level-2	7.413 (5.627-9.767)	1.821 (1.010-3.285)	1.010 (0.417-2.446)
Level-1	83.483 (80.459-86.622)	83.721 (80.686-86.870)	81.485 (78.303-84.795)
Intraclass correlation	0.082	0.021	0.012
N residents	5962	5962	5075
N programs	300	300	237
Likelihood ratio test vs. linear model (x2)	172.20	18.29	6.94
P value	P<0.001	P<0.001	P=0.004

Data: 2019 (version 2) and 2018 ABSITE Survey data. The dependent variable is an IRT-derived burnout T-score based on 6 survey items corresponding to emotional exhaustion and depersonalization subscales (2019 ABSITE survey items Q15A-Q15F, see §E.1 for details). Program strata refers to program quartile based on program mean 2018 ABSITE burnout T-scores. The 5th stratum contains programs that had missing 2018 ABSITE data and were thus not ranked in a quartile. However, this stratum dropped out of the adjusted model due to collinearity.

